13.2.2 Neurocognitive Testing (Bayley-III)

The change in each composite score from baseline will be assessed at each scheduled visit. The three composite measures are cognitive, language, and motor. Only subjects less than 30 months of age are considered.

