Subjects who are responsive to Kuvan will continue to receive once a day doses of 20 mg/kg Kuvan orally. A Kuvan-responsive subject is defined as a subject with $\geq 30\%$ average reduction in blood Phe concentration calculated by the mean of the weekly percent change from baseline in blood Phe concentration at Weeks 1, 2, 3 and 4. The baseline blood Phe concentration is calculated as the mean of the results from Screening visit and at Week 0 (prior to dosing with Kuvan). At the discretion of the Investigator, the subject's daily Phe intake may be modified if blood Phe concentration falls below 120 $\mu\text{mol/L}$ during the study. Kuvan dose may also be reduced after Week 5 after consultation with the Medical Monitor, in subjects who do not tolerate the 20 mg/kg/day dose.

Neurocognitive testing will be performed within 6 weeks of determination of Kuvan responsiveness in all Kuvan-responsive subjects. The types of neurocognitive tests used (Bayley Scales of Infant and Toddler Development®-Third Edition [Bayley-III], Wechsler Preschool and Primary Scale of Intelligence™-Third Edition [WPPSI-III], and/or Wechsler Intelligence Scale for Children®-Fourth Edition [WISC-IV]) will be those appropriate for the subject's current age at assessment. Table 3.2.1 shows the neurocognitive test to be used according to subject age.

	SAP PKU-015, Version 3.0	Page 8 of 31
---	--------------------------	--------------

Table 3.2.1: Neurocognitive Assessments

Age Group	Infancy	Preschool		School-Age
Assessment	Bayley-III	WPPSI-III (First Form)	WPPSI-III (Second Form)	WISC-IV
Age	0 months through < 30 months	30 months through < 4 years	≥ 4 years through < 7 years	≥ 7 years and older
Frequency	Every 6 months ± 2 weeks	Once a year ± 2 weeks	Once a year ± 2 weeks	Every 2 years ± 2 weeks

Growth, blood Phe concentration, and safety will be monitored. These and the neurocognitive assessments will be performed every 6 to 24 months, depending on the type of assessment, until the end of the study.

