4.5 Visit Window for Analysis

The baseline blood Phe concentration is defined as the mean of the screening and Week 0 (prior to dosing with Kuvan) result. Baseline measurement for other assessments is defined as the latest non-missing measurement prior to the first study drug administration in Part 1. If there are two or more measurements within an analysis visit window, the measurement that is closest to the scheduled time point will be used for analyses. If the two closest measurements to the scheduled time point are equidistant from that scheduled analysis time point, the average (or more conservative) of the two assessments will be used for analyses.

Table 4.5.1 presented below defines visit windows for the scheduled analysis time points by analysis parameter.

	SAP PKU-015, Version 3.0	Page 13 of 31
---	--------------------------	---------------

Table 4.5.1: Visit Windows

Assessment	Scheduled Time Point	Visit Window
Bayley-III	Baseline	First measurement date after determination of Kuvan responsiveness (Day 30 to Day 120)
	Month 6	Day 121 to Day 273
	Month 12	Day 274 to Day 456
	Month 18	Day 457 to Day 638
	Month 24	Day 639 to Day 821
WPPSI-III, WISC-IV (based on Month 2 occurrence)	Baseline	First measurement date after determination of Kuvan responsiveness at Month 2 visit (Day 30 to Day 120)
	Month 12	Day 121 to Day 548
	Month 24	Day 549 to Day 913
	Month 12 *i , where $i=2,3,4,5,6,7,\dots$	Day $365*i - 181$, Day $365*i + 183$
WPPSI-III, WISC-IV (based on first assessment)	Baseline*	First measurement date after determination of Kuvan responsiveness
	Month 12	Day 2 to Day 548
	Month 24	Day 549 to Day 913
	Month 12 *i , where $i=2,3,4,5,6,7,\dots$	Day $365*i - 181$, Day $365*i + 183$
Height, head circumference, physical exam	Baseline	Last measurement date prior to the initial study drug administration
	Week 4	Day 2 to 76
	Month 3	Day 77 to Day 137
	Month 6	Day 138 to Day 273
	Month 12	Day 274 to Day 456

	SAP PKU-015, Version 3.0	Page 14 of 31
---	--------------------------	---------------

Assessment	Scheduled Time Point	Visit Window
	Month 18	Day 457 to Day 638
	Month 24	Day 639 to Day 821
	Month 6*i, where i=2,3,4,5,6,7,...	Day $\text{round}(182*i + i/2) - 91$, Day $\text{round}(182*i + i/2) + 91 - \text{mod}(i,2)^*$
Tryptophan, tyrosine	Baseline	Last measurement date prior to the initial study drug administration
	Week 4	Day 2 to 76
	Month 3	Day 77 to Day 137
	Month 6	Day 138 to Day 273
	Month 12	Day 274 to Day 548

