7 DEMOGRAPHICS AND BASELINE CHARACTERISTICS

Subject demographics (age, sex, ethnicity, and race) and baseline characteristics (weight, height, head circumference, blood Phe concentration, prescribed dietary Phe, and blood tryptophan and tyrosine concentration) will be summarized separately by age group at enrollment and all ages combined. A separate table will summarize the neurocognitive testing (Bayley-III, WPPSI-III and WISC-IV) at Month 2 in Part 2.

Age, sex, ethnicity, and race will be summarized using the number and percentage of subjects with a particular attribute. The denominators for percentages will be based on the number of subjects in each age group. Weight, height, head circumference, blood Phe concentration, blood tryptophan and tyrosine concentration, and neurocognitive tests will be summarized using descriptive statistics including n, mean, SD, median, min, max, 25th percentile, 75th percentile. In addition, the percentile and z-scores of weight, height, and head circumference based on CDC Clinical Growth Charts (WHO Growth Charts for subjects less than 2 years of age) will be summarized using descriptive statistics.

A subject listing of demographics and baseline characteristics will also be provided.

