13 EFFICACY EVALUATIONS

Unless specified otherwise efficacy analyses will be based on the efficacy population. The efficacy results will be presented by age group at Screening and by all ages combined, except for the neurocognitive assessments.

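### Bayley-III mean changes by visit come from children who were progressively younger at entry, so they cannot be read as a time course on treatment

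*SAP*

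**What the plan says.** - **Endpoint.** Bayley-III in children under 30 months is a secondary efficacy variable (SAP 13.2). The analysis in 13.2.2 reads: "The change in each composite score from baseline will be assessed at each scheduled visit". It then limits the analysis: "Only subjects less than 30 months of age are considered". It does not say at which time point that age is taken.
- **Who is tested.** Under SAP 3.2 the tests used "will be those appropriate for the subject's current age at assessment". Table 3.2.1 gives Bayley-III at "0 months through < 30 months", with frequency "Every 6 months ± 2 weeks". From 30 months the child moves to WPPSI-III.
- **Windows.** In Table 4.5.1 the Bayley-III baseline is "First measurement date after determination of Kuvan responsiveness (Day 30 to Day 120". Follow-up windows open on Day 121 (Month 6), Day 274 (Month 12), Day 457 (Month 18) and Day 639 (Month 24). Day 1 is the first dose in Part 1 (4.4). Section 7 places the first neurocognitive test at Month 2: "A separate table will summarize the neurocognitive testing (Bayley-III, WPPSI-III and WISC-IV) at Month 2 in Part 2".
- **Presentation.** Section 13 presents efficacy by age group and "by all ages combined, except for the neurocognitive assessments"; Section 4.2 has a matching exception.
- **Missing data.** Efficacy data are not imputed (4.7).

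**The concern.** The visit schedule counts from first dose, while the test ends at a fixed age. A change at a given visit is therefore possible only for a child young enough at entry to be still under 30 months then. The set of children shrinks from the older end at each visit by design, without any dropout.

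A reader given four visit means will naturally see a course over time on treatment. Part or all of any trend could come from the changing mix of entry ages, and no Bayley-III summary by entry age is planned that would reveal it. Bayley-III is the only neurocognitive measure before 30 months, so this is the only evidence on the youngest children. It carries no test or success rule, so the issue is interpretation and not a trial decision.

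**Working it through.** The SAP gives no number, attrition or power for Bayley-III, so there is no figure of its own to reproduce here. Its one sizing figure, 45 subjects, concerns FSIQ and has no bearing on this point.

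**1. Entry-age limit at each visit.** A test on Day d falls d − 1 days after first dose. One month is 365.25/12 = 30.44 days. The latest entry age that still allows Bayley-III is

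30 − (d − 1)/30.44 months.

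Example, Month 6 on scheduled Day 183: 30 − 182/30.44 = 24.0. On the first window day, Day 121: 30 − 120/30.44 = 26.1.

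| Visit | Scheduled day | Limit (months) | First window day | Limit (months) |
|---|---|---|---|---|
| Month 6 | 183 | 24.0 | 121 | 26.1 |
| Month 12 | 366 | 18.0 | 274 | 21.0 |
| Month 18 | 548 | 12.0 | 457 | 15.0 |
| Month 24 | 731 | 6.0 | 639 | 9.0 |

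With the 2-week allowance in Table 3.2.1 (test 14 days early), the Month 6 limit is 24.5 months and the Month 24 limit 6.5 months.

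**2. Share able to contribute.** Assume entry age uniform from 0 to 28 months among children with a Bayley-III baseline. Dividing each limit by 28 gives about 86%, 64%, 43% and 21% on scheduled days, and 93%, 75%, 54% and 32% on first window days. On scheduled days the mean entry age is half the limit: 12, 9, 6 and 3 months.

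**3. Baseline but no follow-up.** Thirty months is 913.1 days. A baseline on Day 61 (Month 2) needs entry before 913.1 − 60 = 853.1 days of age. The share lost is the gap in days between baseline and first follow-up, divided by 853.1:

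- follow-up on the first Month 6 window day (Day 121): 60/853.1 = 7.0%
- follow-up on scheduled Month 6 (Day 183): 122/853.1 = 14.3%
- retest 6 months after the baseline test (Day 244): 183/853.1 = 21.5%

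These figures vary the timing only. Baseline timing also matters: with follow-up on scheduled Month 6, a baseline between Day 120 and Day 30 gives 7.9% to 17.3%. So does the age mix: with a Month 2 baseline and scheduled Month 6, the share is 8.2% if the entry-age density falls 3:1 from 0 to 28 months, and 18.4% if it rises 1:2.

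**4. What composition alone can do (hypothetical).** Suppose the change runs linearly from 0 for entry at birth to −8 for entry at 28 months, and no child changes after Month 6. The visit mean is −8/28 × mean entry age.

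- Scheduled days (mean entry age 12, 9, 6, 3): −3.4, −2.6, −1.7, −0.9
- First window days (half the limits in step 1): −3.7, −3.0, −2.1, −1.3

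That is an apparent recovery of about 2.6 or 2.4 points in which no child recovered. The gradient is invented. It shows the mechanism and its direction, and says nothing about its real size.

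**The case against.** Several stronger readings are tempting, and the SAP does not support them.

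- **That a fixed share, such as 14%, can never have a change score.** That figure needs uniform entry age, a Month 2 baseline and follow-up on the scheduled day. A child entering at 24 to 26 months can still be tested early enough to fall in the Month 6 window.
- **That Month 24 holds only children who entered before 6 months.** This is true on the scheduled day, but the window opens on Day 639 and admits entry up to about 9 months.
- **That the endpoint has no interpretable overall answer.** Any child young enough for Month 12, 18 or 24 was also young enough for Month 6. Apart from missed tests, the Month 6 summary gives one change per child for nearly all who can have one.
- **That children who reach 30 months are lost.** They move to WPPSI-III, and their FSIQ scores can enter the primary analysis.

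It is also fair to say that Section 4 already requires the number of observations with each summary, and that 13.2 provides a listing. The falling n will therefore be visible. The change in entry age behind it will not be, unless the reader works through the listing.

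Finally, the exception in Sections 4.2 and 13 could be read as removing only the combined-age presentation. Section 13.3.1 presents IQ by sequence and overall, and 13.2.2, unlike 13.2.1 for growth, names no age groups. Exemption from the age-group split is thus the more natural reading. Either way, the wording for Bayley-III needs settling.

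**Conclusion.** The point holds as one of interpretation. With a test that ends at 30 months, visits counted from first dose, no imputation and no entry-age split, Bayley-III means at successive visits describe different children, each set younger at entry than the last. Comparing those means confounds time on treatment with entry age. Even on the most generous window day, Month 24 excludes anyone who entered after about 9 months.

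The entry-age limits follow from the SAP's own schedule and windows. The share with a baseline and no follow-up, roughly 7% to 21%, rests on a Month 2 baseline and an assumed uniform entry age, and moves with both. The Month 6 result stands. Because Bayley-III is a secondary endpoint with no success rule, this should be corrected but does not threaten the primary conclusion.

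**What to change.** Amend 13.2.2, with a matching change to the exception in 4.2 and Section 13:

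1. State that the 30-month limit applies at the time of each test.
2. Lift the exception for Bayley-III and show by-visit changes by entry age, using the 0 to <1 and 1 to <2 year groups already defined in 4.2, with n and entry age at each visit. On the scheduled days, children entering at 2 years or older would have no change scores.
3. Restrict any comparison across visits to children who contribute to all the visits compared. On the nominal schedule, children entering under 1 year allow this through Month 18. Month 24 again narrows to the youngest entrants, and the 1 to <2 year group narrows already at Month 12.
4. Count children with no later Bayley-III because they reached 30 months separately from dropouts.

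The change to the last Bayley-III should not serve as the overall result. With a Month 2 baseline on the scheduled days, its interval would be about 22, 16, 10 or 4 months for entry at under 6, 6 to 12, 12 to 18 or 18 to 24 months, which ties duration to entry age again.

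The cost is SAP wording and extra table rows from data already planned for collection. The small downside is small cells.

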13.3 Exploratory analyses

Exploratory variables include:

- IQ scores
- Blood Phe concentration
- Relationship between neurocognitive testing and blood Phe
- Prescribed dietary Phe

A subject listing of IQ scores, neurocognitive testing results, blood Phe, and prescribed dietary Phe will be provided.

	SAP PKU-015, Version 3.0	Page 23 of 31
---	--------------------------	---------------

13.3.1 IQ Scores

An exploratory analysis to assess the effect of blood Phe control with Kuvan on IQ over a 7 year observation period will examine the stability from baseline in the FSIQ score. Baseline for FSIQ score is defined as the first assessment in FSIQ score after determination of Kuvan responder status. The analysis will be performed using a repeated measures model with factors visit and testing sequence, with change in FSIQ score as the dependent variable. The model will apply an unconstructed covariance matrix unless another covariance structure provides a better model fit. 95% Confidence intervals will be reported annually with emphasis at Year 7. A figure of LS-means and the 95% CI will also be displayed.

Specific subsets are summarized to further examine the robustness of the above Year 7 results. The following subsets will be used:

- Subjects enrolled in study due to an exemption are excluded
- Subjects with a Baseline FSIQ score at the recommended visit (Month 2)
- Subjects assigned to Sequence 2 with Baseline as the first assessment in FSIQ score after determination of Kuvan responder status
- Subjects assigned to Sequence 2 with Baseline as the first assessment in FSIQ score at the recommended visit (Month 2)

All subset summaries include a repeated measure analysis similar to the original analysis. Sequence is removed from the analyses where the subset is based on sequence.

Furthermore, the mean change from baseline in FSIQ score at Year 7 will be summarized descriptively by sequence and overall. A paired t-test will be performed across all subjects with a 95% CI and p-value reported at Year 7. An additional subset examining subjects without a Baseline FSIQ score at the recommended visit (Month 2) is presented as well.

In addition, descriptive statistics of each observed composite and subtest IQ score and its respective change in IQ score from Baseline will also be presented by sequence and overall and listed at each time point. The change from Baseline of each composite score will be plotted as well.

Proportion of subjects with a specified change from Baseline in each composite and subtest IQ will also be summarized at each time point. The specific change is as follows:

	SAP PKU-015, Version 3.0	Page 24 of 31
---	--------------------------	---------------

- FSIQ: absolute change greater than 7
- Verbal IQ: absolute change greater than 10
- Performance IQ: absolute change greater than 10
- Each subtest: absolute change greater than 3

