13.1 Primary Efficacy Endpoint

The primary efficacy variable is the FSIQ score measured by the WPPSI-III or WISC-IV tests. The primary efficacy endpoint is the change in the FSIQ score over a 2 year period. A random coefficient model is used to calculate the slope (per year) of FSIQ over the entire study period and for each subject. Factors in the model will include visit and testing sequence, with change in FSIQ score as the dependent variable. Random terms include both intercept and visit. The model will use an unconstructed covariance matrix unless another covariance structure provides a better model fit. Subjects with less than one year of treatment duration are excluded from the analysis. Once the slope and 95% confidence interval are derived, the slope and lower limit of the confidence interval are multiplied by 2 to determine the average change in FSIQ and its lower limit over a 2-year window. The treatment will be considered successful if the lower 95% confidence limit of the mean change excludes a decline of greater than 5 points over a 2-year window.

All available data will be included in the analysis and the analysis will be stratified by testing sequence.

- Sequence 1: WPPSI-III (first or second form) at all time points
- Sequence 2: WPPSI-III (first or second form) at Baseline and (WPPSI-III or) WISC-IV at all post-baseline time points
- Sequence 3: WISC-IV at all time points

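### Does the two-yearly WISC-IV schedule make the unstructured covariance in the exploratory FSIQ model (SAP 13.3.1) unworkable and the Year 7 result unreliable?

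*SAP*

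**What the plan says.** SAP section 13.3.1 describes an exploratory repeated measures model with visit and testing sequence as factors and change in FSIQ as the response. On the covariance it says: "The model will apply an unconstructed covariance matrix unless another covariance structure provides a better model fit". The printed word is a slip for unstructured. On reporting it says: "95% Confidence intervals will be reported annually with emphasis at Year 7". On the time origin it says: "Baseline for FSIQ score is defined as the first assessment in FSIQ score after determination of Kuvan responder status".

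Table 3.2.1 in section 3.2 gives WPPSI-III once a year from 30 months to under 7 years. From age 7 it gives WISC-IV "Every 2 years ± 2 weeks". Table 4.5.1 uses annual FSIQ windows counted from the first assessment.

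Beside the model, section 13.3.1 plans Year 7 descriptive statistics by sequence and overall, a paired t-test at Year 7 across all subjects, and subset models. Two of those are confined to Sequence 2, with sequence dropped as a factor. The primary analysis in section 13.1 is a separate random-coefficient slope model.

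**The concern.** Annual visits in the model and two-yearly tests in the schedule do not fit together. Once a child moves to WISC-IV, the tests fall either in odd or in even years after the first FSIQ, not in both. An unstructured matrix needs children observed at both visits of every pair, and for some late pairs there are none.

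The covariance clause speaks of a better fit. It lists no candidate structures, no criterion and no action for a singular or non-converging fit. The structure might then be chosen after the data are seen. The emphasised visit, Year 7, also lies in the thinned part of the schedule. At stake would be the credibility and precision of the 7-year stability result.

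**Working it through.** **1. The plan's own figure.** Section 3.4 gives SD 16, correlation 0.8, n = 45, two-sided 0.05 and a margin of 2 × 2.5 = 5 points.
- SD of change = 16 × √(2 × (1 − 0.8)) = 10.12.
- Power = Φ(5/(10.12/√45) − 1.96) = Φ(1.35) = 91.2%, or 90.0% with the noncentral t.

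The stated 90% reproduces. It belongs to the primary endpoint; only the SD of change is used below.

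**2. Where Year 7 lies.** The window runs from Day 365 × 7 − 181 = 2374 to Day 365 × 7 + 183 = 2738. Day 2374 is 6.5 years after a first FSIQ at age 2.5 or later, so the child is at least 9.0 years old. Every scheduled Year 7 test is a WISC-IV.

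**3. Which years are tested.** The SAP does not state how the first WISC-IV is anchored, which may be left to the protocol, so several readings were tried. Years are counted from the first FSIQ.

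| Age at first FSIQ | First WISC-IV 1 year after last WPPSI-III | 2 years after |
|---|---|---|
| 2.5 to <3 | 1,2,3,4,5,7 | 1,2,3,4,6 |
| 3 to <4 | 1,2,3,4,6 | 1,2,3,5,7 |
| 4 to <5 | 1,2,3,5,7 | 1,2,4,6 |
| 5 to <6 | 1,2,4,6 | 1,3,5,7 |
| 6 to <7 | 1,3,5,7 | 2,4,6 |

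- First reading: Year 7 is tested in (0.5 + 1 + 1)/4.5 = 55.6% of first-test ages. Pairs never seen together: (5,6) and (6,7).
- Second reading: (1 + 1)/4.5 = 44.4%. Pairs never seen together: (4,5), (4,7), (5,6) and (6,7).
- WISC-IV at the seventh birthday: 44.5%. Pairs never seen together: (5,6) and (6,7).

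Seven visits give 7 × 8/2 = 28 elements, of which 26, 24 and 26 can be estimated. The ±2-week tolerance adds the (6,7) pair in at most 0.5% of children.

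**4. Effect on the Year 7 estimate.** A child's likelihood contribution uses only the part of the matrix for visits that the child has. A covariance between two visits that no child shares appears nowhere. As a check, generalised least squares was run on 63 children with the first-reading patterns, variance of change 102.4 and correlation 0.5 between changes. The (5,6) and (6,7) covariances were set to 0, 25, 51.2 and 80. The Year 7 SE was 1.57 each time.

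**5. Precision at Year 7.** Assume 45 children with entry ages uniform over 0 to 7.
- Followed 7 years from first FSIQ: 0.286 × 45 ≈ 13 (second reading) to 0.690 × 45 ≈ 31 (first reading) have a Year 7 test.
- Followed 7 years from start of treatment: about 13 to 16. Even yearly testing would then give only 0.667 × 45 ≈ 30, because young entrants have no FSIQ before 30 months.
- Paired-t half-width, t × 10.12/√n: 6.1 at n = 13, 5.4 at n = 16, 3.8 at n = 30.
- The repeated measures model also borrows from earlier visits. With compound symmetry, known covariance and visit effects only, the Year 7 SE is 2.45 with 13 children at Year 7, against 10.12/√13 = 2.81 for the paired analysis. With 31 children it is 1.71, against 10.12/√31 = 1.82.

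**6. Cost of keeping the unstructured matrix.** In a simulation with about 27 children at Year 7 and data generated under compound symmetry, unstructured 95% intervals covered about 89-91%. Compound symmetry covered about 95%.

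**The case for a change.** The strongest case for a change is that the SAP's first-choice matrix cannot be fully estimated from its own schedule, and that this was foreseeable. A comparison of fit is awkward when the first-choice model has parameters absent from the likelihood. Software may report a singular Hessian or fail on a degrees-of-freedom correction. The paired t-test avoids the covariance but uses the same thin Year 7 group. The simulation shows that insisting on the unstructured matrix would cost some coverage.

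The schedule argument stands, and so does the absence of a named criterion. The rest is weaker. The clause permits a simpler structure, and in the simulated setting the simpler structure restores coverage. Off-schedule tests could add only a few of the missing pairs, but nothing depends on them.

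A related worry is the weight of the three testing sequences in the Year 7 LS-mean, since only "Sequence 2: WPPSI-III (first or second form) at Baseline and (WPPSI-III or) WISC-IV at all post-baseline time points" has scheduled Year 7 tests. It rests on an assumed equal weighting. Without a visit-by-sequence interaction, which the SAP does not name, sequence effects are estimated from all visits, so Year 7 data in each sequence are not required. The planned Sequence 2 models address the point directly.

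Imposing one restrictive covariance could misstate standard errors. Merging Years 6 and 7 would mix two lengths of follow-up. Its apparent half-width of 3.0 at n = 45 needs every child to reach Year 6; with 7 years of treatment about 28-37 of 45 would have a Year 6 or Year 7 test, giving about 3.4 to 3.9. Both are debatable trades.

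**Conclusion.** No change to the plan follows. The schedule leaves two to four of 28 covariance elements without scheduled data, and about 44-56% of first-test ages have a Year 7 test. Both follow from the two-yearly WISC-IV interval, which is a testing schedule and not an analysis error. The gaps are planned, so they do not in themselves bias the Year 7 mean, and the missing elements do not affect its model-based SE. Precision at Year 7 is limited, and part of that comes from the first FSIQ being possible only at 30 months.

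What remains is an unwritten fallback order and fit criterion in an exploratory model with no success rule. The clause already allows the switch a competent analyst would make, the paired t-test stands beside the model, and the primary slope is untouched.

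The shares of children assume uniform entry ages, since the SAP gives no age distribution. The pairs never observed together do not depend on that assumption. The precision and coverage figures assume the SAP's SD and correlation or compound symmetry.
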